6.2.2 Treatment period(s)

For Part A, masking is not required for the IVT injection preparation or administration. For Part B, IVT injection will be prepared by the unmasked pharmacist/qualified person (Section 4.1.6). In addition, an unmasked injector (Section 4.1.6) with no other involvement in the trial will administer either active or sham injection according to the treatment assigned by IRT. IVT injections must be carried out according to medical standards and applicable guidelines by a qualified physician experienced in administering IVT injections and will be done as part of drug administration visit procedures (Visit 2 for Part A and Visits 2, 3 and 4 for Part B) after the other ophthalmologic assessments in the [Flow Chart I](#) and [Flow Chart II](#) have been performed (please see Section 4.1 for details).

6.2.3 Follow-up period and trial completion

Subjects must continue to be followed according to the visit schedule (unless they withdraw consent for further follow-up) in order to collect data at the end of the planned observation period. Unscheduled visits will be possible at the discretion of the investigator at any time for safety reason. The unscheduled visit may include any assessments considered necessary by the investigator. All unscheduled visits should be described and documented in the medical /source record. The investigator may decide other treatment options during the follow-up period as deemed medically appropriate.

Part A

Visit 8/End of Study:

The Visit 8/EOS will be performed 42 days after Visit 7 (see [Flow Chart I](#)).
The Visit 8/EOS is the final visit and the End of Study eCRF has to be completed.

Part B

Visit 7/End of Study:

The Visit 7/EOS will be performed 28 days after Visit 6 (see [Flow Chart II](#)).
The Visit 7/EOS is the final visit and the End of Study eCRF has to be completed.

Withdrawal of consent

Every effort should be made to keep the subject in the trial and undergoing the procedures and follow up as outlined in the Flow Charts I and II and Section [6.2.3](#).

If a subject is not willing to continue in the trial and wants to withdraw consent prior to the end of the study, Visit 7 (Part A)/ Visit 6 (Part B) should be scheduled as soon as possible, and also Visit 8/EOS(Part A)/ Visit 7/EOS(Part B) should be performed to assess for safety.

The End of Study eCRF has to be filled in even if subject refuses to participate to the above specified visits.

For AE assessment, laboratory tests, recording of ECG and vital signs, and physical examination during the follow-up period, see Section [5.2](#).

Subjects who discontinue treatment before the end of the planned treatment period should undergo the EOS Visit.

All abnormal values (including laboratory parameters) that are assessed as clinically relevant by the investigator will be monitored using the appropriate tests until a return to a medically acceptable level is achieved. (S)AEs persisting after a subject's EOS Visit must be followed until they have resolved, have been sufficiently characterised, or no further information can be obtained.

7. STATISTICAL METHODS AND DETERMINATION OF SAMPLE SIZE

The objective of this trial is to determine the safety and tolerability of BI 765128 in panretinal photocoagulation (PRP) treated diabetic retinopathy (DR) patients with diabetic macular ischemia (DMI), based on the primary endpoint, the occurrence of dose limiting events (DLE) (see Section 5.2.1) in the 7 days post administration (Part A) or the occurrence of drug-related AEs until EOS (Part B). The safety, tolerability and early biological response after multiple IVT injections of BI 765128 will also be investigated.

7.1 STATISTICAL DESIGN – MODEL

This trial will consist of a Part A followed by a Part B. The Part A will be conducted non-randomized, open-label, and uncontrolled. Part B will be conducted double-masked randomized and sham-controlled.

Part A:

The dose escalation will be guided by a Bayesian 2-parameter logistic regression model with overdose control [R13-4803, R13-4806].

The model is given as follows:

$$\text{logit}(\pi_d) = \log(\alpha) + \beta \cdot \log(d/d^*),$$

where $\text{logit}(\pi) = \log(\pi/(1-\pi))$, π_d represents the probability of having a DLE in the evaluation period at dose d , $d^* = \blacksquare$ mg is the reference dose, allowing for the interpretation of α as the odds of a DLE at dose d^* , and $\theta = (\log(\alpha), \log(\beta))$ with $\alpha, \beta > 0$ is the parameter vector of the model.

The estimated probability of a DLE at each dose level from the model will be summarized using the following intervals:

Target toxicity: [0.00, 0.25)

Over toxicity: [0.25, 1.00]

The BLRM-recommended dose for the next cohort is the highest dose level with posterior probability of the DLE rate falling in the target interval [0.00, 0.25) among the doses fulfilling EWOC. Thus, applying the EWOC criterion it should be unlikely (< 25% posterior probability) that the DLE rate at that dose will exceed 0.25. However, the allowed dose increment will always be the next higher pre-planned dose. However, the maximum allowable dose increment for the subsequent cohort will be no more than 250% from the previous dose. Dose escalation will continue up to the \blacksquare dose as long as the EWOC criterion for the next dose level is fulfilled. At the final dose, at least 6 treated subjects are required. However, the SMC may decide to include additional number of subjects at this dose level.

Since a Bayesian approach is applied, a prior distribution $f(\theta)$ for the unknown parameter vector θ needs to be specified. This prior distribution will be specified as a mixture of three multivariate normal distributions, i.e.

$$f(\theta) = a_1 f_1(\theta) + a_2 f_2(\theta) + a_3 f_3(\theta)$$

with a_i , $i = 1, 2, 3$ the prior mixture weights ($a_1 + a_2 + a_3 = 1$), and $f_i(\theta) = \text{MVN}(\mu_i, \Sigma_i)$, the multivariate normal distribution of the i -th component with mean vector μ_i and covariance matrix Σ_i , where

$$\Sigma_i = \begin{pmatrix} \sigma_{i,11}^2 & \sigma_{i,11}\sigma_{i,22}\rho_i \\ \sigma_{i,11}\sigma_{i,22}\rho_i & \sigma_{i,22}^2 \end{pmatrix}.$$

Mixture prior distributions have the advantage that they allow for specification of different logistic dose-toxicity curves, therefore making the prior more robust.

For the current study, no relevant information in the form of human data is available, since no study in a comparable population has been conducted. Therefore, the three mixture components were established as follows:

1. A weakly informative prior was derived reflecting the a priori assumption that the median DLE rate at the starting dose of [REDACTED] would equal 0.02, and the median DLE rate at the maximum dose of [REDACTED] would equal 0.1. This yields $\mu_1 = (-2.197, 0.052)$. The standard deviations were set such that medium uncertainty about the parameter means is reflected, and the correlation was set to 0, thus yielding $\sigma_{1,11} = 1.2$, $\sigma_{1,22} = 1.5$ and $\rho_1 = 0$, respectively. The prior weight a_1 for the first component was chosen as 0.9.
2. A high-toxicity weakly informative prior was derived reflecting the case that the compound would be much more toxic than expected. For this prior component, it was assumed that the median DLE rate at the starting dose of [REDACTED] would equal 0.1, and the median DLE rate at [REDACTED] would equal 0.3. These assumptions yield $\mu_2 = (-0.847, -0.176)$. The standard deviations and correlations were such that large uncertainty about the parameter means is reflected, and the correlation was set to 0, thus yielding $\sigma_{2,11} = 2$, $\sigma_{2,22} = 1$ and $\rho_2 = 0$, respectively. The prior weight a_2 for the second component was chosen as 0.05.
3. A low-toxicity weakly informative prior was derived reflecting the case that the compound would be much less toxic than expected. For this prior component, it was assumed that the median DLE rate at the starting dose of [REDACTED] would equal 0.001, and the median DLE at [REDACTED] would equal 0.01. These assumptions yield $\mu_3 = (-4.595, 0.362)$. The standard deviations and correlations were set to $\sigma_{3,11} = 2$, $\sigma_{3,22} = 1$. The correlation was set to 0, i.e. $\rho_3 = 0$. The prior weight a_3 for the third component was chosen as 0.05.

A summary of the prior distribution is provided in Table 7.1: 1. Additionally, the prior probabilities of DLEs at different doses, as well as the corresponding probability of targeted and overdosing, are shown in Table 7.1: 2. Graphically, the prior medians with accompanying 95% credible intervals are shown in Figure 7.1: 1. As can be seen from both Table 7.1: 2 and Figure 7.1: 1, the prior medians of the DLE probabilities are in line with the prior medians derived from the weakly informative prior, and the uncertainty around the medians is relatively large, showing the medium amount of information this prior provides. This is also supported by the prior sample size, i.e. the information contained in the prior. This is approximately equal to 3.7 subjects. A detailed evaluation of the model using hypothetical data scenarios and operating characteristics is provided in Appendix 10.3.

Table 7.1: 1 Summary of prior distribution

Prior Component	Mixture Weight	Mean Vector	SD Vector	Correlation
1: Weakly inf.	0.900	-2.197, 0.052	1.2, 1.5	0
2: High Tox.	0.050	-0.847, -0.176	2, 1	0
3: Low Tox.	0.050	-4.595, 0.362	2, 1	0

Table 7.1: 2 Prior probabilities of DLEs at selected doses

Dose	Probability of true DLE rate		mean	sd	Quantiles		
	(0-0.25]	[0.25-1]			2.50%	50%	97.50%
	0.950	0.050	0.054	0.104	0.000	0.013	0.361
	0.927	0.073	0.073	0.120	0.000	0.027	0.428
	0.810	0.190	0.153	0.160	0.006	0.098	0.608

Median (95% CrI)

[figure not shown]

Figure 7.1: 1 Prior medians and 95% credible intervals

The prior may be updated once the trial has started in case new data that can be used will be available. Only subjects for which the occurrence of DLEs within the evaluation period can be evaluated will be considered. The prior that is used for each BLRM analysis for the SMC meetings will be documented in the SMC minutes, the prior used for the final analysis will be documented in the TSAP in case a different prior than described above will be used.

The MFD may be considered reached if all of the following criteria are fulfilled:

- Next recommended dose by the BLRM = current dose
- At least 12 subjects have been treated in the trial.
- At least 6 subjects have been treated at the MFD.

Part B:

The size of the foveal avascular zone (FAZ) is associated with visual loss. Measuring FAZ by OCTA is highly reproducible. The assumed treatment effect of BI 765128 (reduction in the area of FAZ) as compared with sham treatment after 3 months of treatment is 10%. Showing this reduction in size of FAZ is believed to be clinically relevant.

Only 1 dose, the highest dose, of Part A will be used for Part B, the MD study. The highest dose is usually limited by the maximum dose possible in the IVT injectable volume.

7.2 NULL AND ALTERNATIVE HYPOTHESES

No confirmatory testing is performed and hence no null and alternative hypotheses are defined. Any confidence intervals computed are to be interpreted in the perspective of the exploratory character of the study; i.e., confidence intervals are considered as interval estimates for effects. A discussion of the sample size is provided in Section [7.6](#).

7.3 PLANNED ANALYSES

7.3.1 Subject analysis sets

The main analysis populations are defined below. In the TSAP, further analysis data sets may be defined. Subjects will be analysed according to the assigned treatment, unless otherwise specified.

Important protocol deviations (IPD) categories will be defined in the IPD specification document. IPDs will be identified no later than in the Report Planning Meeting, and the IPD categories will be updated as needed. The handling of subjects with IPDs will be described in the TSAP.

Treated set (TS)

For part A the treated set includes all subjects who were treated with at least one dose of study drug.

For part B the treated set includes all subjects who were randomized and treated with at least one dose of study drug (either treatment with BI 765128 or Sham).

7.3.2 Primary endpoint analyses

Part A:

The primary safety endpoint “Number of subjects with ocular (in the study eye) DLEs from drug administration till day 7” will be analysed descriptively, based on the TS.

Part B:

The primary safety endpoint “Number of subjects with drug-related AEs from drug administration until EOS” will be analysed descriptively, based on the TS.

7.3.3 Secondary endpoint analyses

The secondary endpoints (refer to Section [2.1.3](#)) will be summarized by means of descriptive statistics (at least n, mean, standard deviation, median, minimum and maximum) for continuous variables or frequency tables for categorical variables. The change from baseline (in mm²) of FAZ will be analysed using a generalized mixed linear model (for details refer to the TSAP). The endpoint Central retinal thickness (µm) will be analyzed in the same way as the endpoint FAZ. In addition, the BCVA will be analyzed using a generalized linear model.

Analyses regarding safety and efficacy will be performed on the TS.

7.3.5 Safety analyses

Adverse events will be coded using the Medical Dictionary for Drug Regulatory Activities (MedDRA). Standard BI summary tables and listings will be produced. For BI 765128, the residual effect period (REP) after IVT administration is not known. Therefore, all AEs with an onset between start of treatment and the respective EOS visit will be assigned to the ontreatment period for evaluation. The safety analysis will be performed by planned dose group.

All treated subjects will be included in the safety analysis. In general, safety analyses will be descriptive in nature and will be based on BI standards. No hypothesis testing is planned.

Statistical analysis and reporting of adverse events will concentrate on treatment-emergent adverse events, i.e. all adverse events occurring between start of treatment and end of the EOS. Adverse events that start before first drug intake and deteriorate under treatment will also be considered as 'treatment-emergent'.

For all analyses the treatment actually administered (= treatment at onset) to the subject will be used (any deviations from the randomized treatment will be discussed in the minutes of the Report Planning Meeting).

Frequency, severity, and causal relationship of adverse events will be tabulated by system organ class and preferred term after coding according to the current version of the Medical Dictionary for Drug Regulatory Activities (MedDRA) at database lock.

Note that AEs occurring after the last per protocol contact but entered before database lock will be reported to Pharmacovigilance only and will not be captured in the trial database (See section [5.2.7.2.1](#)).

Laboratory data will be analysed both quantitatively as well as qualitatively. The latter will be done via comparison of laboratory data to their reference ranges. Values outside the reference range as well as values defined as clinically relevant will be summarised. Treatment groups will be compared descriptively with regard to distribution parameters as well as with regard to frequency and percentage of subjects with abnormal values or clinically relevant abnormal values.

Vital signs, physical examinations, or other safety-relevant data observed at screening, baseline, during the course of the trial and at the end-of-trial evaluation will be assessed with regard to possible changes compared to findings before start of treatment.

Additionally, further treatment intervals (called analysing treatments) may be defined in the TSAP in order to provide summary statistics for other than above periods, such as combined treatments, on-treatment totals, or periods without treatment effects (such as screening and post-study intervals).

The ECG variables QT, HR, QTcF, QTcB, PR, QRS, and RR obtained from the centralised evaluation of 12-lead ECG recordings will be the basis for the derivation of quantitative and categorical ECG endpoints. These endpoints and their analyses will be described in the TSAP.

7.3.6 Other Analyses

In order to characterize BI 765128's exposure-response relationship, a pharmacometric population PKPD analysis may be performed. Furthermore, if data allow, a pharmacometric analysis will be conducted to estimate vitreal concentrations. The pharmacometric analysis will not be part of the CTR but will be provided separately.

7.3.7 Interim Analyses

No interim analysis is planned.

The sponsor will continuously monitor the safety.

Part A

The dose escalation design of the Part A foresees that the sponsor and the SMC perform regular safety evaluations, the SMC will meet after the last subject of each dose cohort has attended Visit 5 (section [3.1](#)) These evaluations will be unmasked to dose.

Part B

The sponsor and the SMC perform one safety evaluation, the SMC will meet after 50% of the subjects were randomized and finished Visit 5. This analysis will involve descriptive and graphical presentation of primary, secondary and further endpoints. These evaluations will be unmasked to dose.

In addition, a fast track analysis will be performed after the final subject of Part B has attended Visit 6 (i.e. approximately 8 weeks after receiving the final dose).

7.4 HANDLING OF MISSING DATA

7.4.1 Safety

Missing baseline laboratory values will be imputed by the respective values from the screening visit. No other imputations will be performed on missing data although every effort will be made to obtain complete information on all AEs, with particular emphasis on potential DLEs.

7.4.3 Efficacy

All data will be analyzed and presented without any form of imputation. For the statistical sensitivity analysis missing values will be imputed using LOCF.

7.5 RANDOMISATION

Part A

Subjects within a cohort receive the same trial medication, therefore no randomization for treatment assignment is performed.

Part B

Subjects will be randomized in a 2:1 ratio (BI 765128: Sham injection).

BI will arrange for the randomisation and the packaging and labelling of trial medication. The randomization list will be generated using a validated system, which involves a pseudo-random number generator so that the resulting treatment will be both reproducible and non-predictable. The block size will be documented in the Clinical Trial Report. Access to the codes will be controlled and documented.

The randomization list will contain additional blocks to allow for subject replacement (refer to Section [3.3.5](#)).

7.6 DETERMINATION OF SAMPLE SIZE

Part A:

No formal statistical power calculations to determine sample size were performed for this explorative study. A Bayesian logistic regression model (BLRM) was used for guiding the dose escalation process (see Section [3.1](#) for details). For the SRD part, a minimum of 3 subjects and a maximum of 18 subjects will be expected for this trial based on the number of dose levels/cohorts that are tested (for details regarding the BLRM assumptions refer to appendix [10.3](#)). Fewer subjects might be needed based on the recommendation of the SMC. However, the actual number of subjects will depend on the number of dose cohorts tested. Based on the simulation study to evaluate operating characteristics of the BLRM, about 15 evaluable subjects are expected to be treated in the dose escalation part for the model to have reasonable operating characteristics relating to its MFD recommendation.

Part B:

In the publication Samara et al. [[R17-3318](#)] estimates for FAZ means and standard deviations (SD) were derived. The worst case was for PDR subjects with mean deep FAZ of 0.766 mm². The standard deviation of FAZ ranged from 0.112 mm² to 0.3402 mm² for disease categories from control to PDR. It is assumed that intra-individual variability is much lower than the inter-individual SD from Samara et al. because of the high correlation of the baseline and the FAZ values after treatment. Taking into account the high correlation, a SD of FAZ of 0.1 mm² seems to be reasonable to be used in calculation of risk probabilities. With 20 subjects in the BI 765128 [REDACTED] arm and 10 subjects in the sham arm, there is a likelihood of 81.7% of observing a treatment effect larger than 6% (a reduction of 0.0462 mm²) and a likelihood of 10.2% of observing a treatment effect smaller than 4% (a reduction of 0.0308mm²) when the assumed mean treatment difference is 10%. Assuming a mean treatment difference of 0% there is a likelihood of 12.3% observing a treatment effect larger than 6% and a likelihood of 78.7% of observing a treatment effect smaller than 4%.

8. INFORMED CONSENT, TRIAL RECORDS, DATA PROTECTION, PUBLICATION POLICY, AND ADMINISTRATIVE STRUCTURE

The trial will be carried out in compliance with the protocol, the ethical principles laid down in the Declaration of Helsinki, in accordance with the ICH Harmonized Guideline for Good Clinical Practice (GCP), relevant BI Standard Operating Procedures (SOPs), the EU directive 2001/20/EC / EU regulation 536/2014 and other relevant regulations. Investigators and site staff must adhere to these principles. Deviation from the protocol, the principles of ICH GCP or applicable regulations as will be treated as “protocol deviation”. Standard medical care (prophylactic, diagnostic and therapeutic procedures) remains the responsibility of the treating physician of the subject.

The investigator will inform the sponsor immediately of any urgent safety measures taken to protect the trial subjects against any immediate hazard, as well as of any serious breaches of the protocol or of ICH GCP.

The Boehringer Ingelheim transparency and publication policy can be found on the following web page: trials.boehringer-ingelheim.com. The rights of the investigator and of the sponsor with regard to publication of the results of this trial are described in the investigator contract. As a rule, no trial results should be published prior to finalisation of the Clinical Trial Report.

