- Next recommended dose by the BLRM = current dose
- At least 12 subjects have been treated in the trial
- At least 6 subjects have been treated at the MFD

Part B of the study will only start if the highest dose is tolerated. Once the last subject in the highest dose cohort of Part A has attended visit 5 (day15) the SMC will meet and evaluate all

DLE data as well as available systemic and ophthalmological safety data. The decision on whether to proceed to Part B will be taken based on the occurrence of DLEs.

Part B:

In Part B, the highest dose will be used (██████). Thirty subjects will be recruited, 2:1 ratio of active treatment versus sham. Subjects dosed in Part A of the trial will not be included.

Subjects will be randomized to receive either active treatment or sham injection.

In Part B, subjects will receive three consecutive doses/sham injections over a 3-month period (██████████). All subjects included in the part B of the trial, will be observed for safety and efficacy for 12 weeks after the last injection.

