10.3 STATISTICAL APPENDIX

A BLRM with overdose control will be used to guide dose escalation in this study. The BLRM is introduced in Section 7.1, which also specifies the prior for the model. After subjects in each cohort have completed the evaluation period, the prior distribution will be updated through Gibbs sampling procedures with the accumulated DLE data from the evaluation period. Posterior probabilities for the rate of DLEs will be summarized from the BLRM. Selection of the next dose will be based on these probabilities as well as on other safety and laboratory data.

The purpose of this statistical appendix is to present performance metrics (operating characteristics) that illustrate the precision of the design in estimating the MFD (see Section 3.1) under various dose-toxicity relationships through computer simulation. These results are summarized in Table 10.3: 3. In addition, recommendations of the next dose level by the BLRM with overdose control principle are provided under various hypothetical outcome scenarios in early cohorts, to show how it facilitates on-study dose-escalation decisions (see Table 10.3: 1). For simplicity reasons, a cohort size of 3 subjects who are all evaluable is assumed.

Hypothetical data scenarios

Hypothetical data scenarios are shown in Table 10.3: 1. These scenarios reflect potential on-study data constellations and related escalation as allowed by the model and the planned dose groups. For each scenario, the probability of overdose for the current dose, as well as the next potential dose and related probabilities of target dosing and over-dosing are shown (probability of over-dosing: P(OD), probability of target dosing: P(TD)).

For example, scenario 1 represents the case that no DLE is observed in 3 subjects at the starting dose of [REDACTED]. In this case, the next planned dose permitted by the model is 1 mg.

In scenario 6, there is no DLE after the first 2 dose groups, which would allow the trial to continue to the next dose level. If no further DLE occurs in the trial (scenario 13), dose escalation would proceed to the [REDACTED] dose, with an additional cohort at that dose level at the end, i.e. overall 12 subjects.

Table 10.3: 1 Hypothetical data scenarios

Scenario	# Pat.	# DLE	[REDACTED]	[REDACTED]	[REDACTED]
1	3	0	[REDACTED]	[REDACTED]	[REDACTED]
2	3	1	[REDACTED]	[REDACTED]	[REDACTED]
3	3	2	[REDACTED]	[REDACTED]	[REDACTED]
4	6	1	[REDACTED]	[REDACTED]	[REDACTED]

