5	6	2	[REDACTED]	[REDACTED]	[REDACTED]

Scenario		# Pat.	# DLE
6		3	0
		3	0
7		3	0
		3	1
7b		3	0
		6	1
7c		3	0
		6	2
8		3	0
		3	2
10		6	1
		3	0
11		6	1
		3	1
11b		6	1
		6	1
11c		6	1
		6	2
12		6	1
		3	2
13		3	0
		3	0
		6	0
14		3	0
		3	0
		6	1
15		3	0
		3	0
		6	2
16		3	0
		6	1
		6	0
17		3	0
		6	1
		6	1
18		3	0
		6	1
		6	2

Scenario	# Pat.	# DLE
19	6	1
	6	1
	6	0
20	6	1
	6	1
	6	1
21	6	1
	6	1
	6	2

*Non of the pre-specified dose levels is fulfilling the EWOC criterion

No higher dose level specified

Operating characteristics

Operating characteristics are a way to assess the long-run behaviour of a model by illustrating the precision of the design in estimating the MFD. Under an assumed true dose-toxicity curve, metrics such as the probability of recommending a dose with true DLE rate in the target interval can be approximated via simulation. Table 10.3: 2 describes 5 assumed true dose-toxicity scenarios which were used to assess the operating characteristics of the model. These scenarios reflect a wide range of possible cases as follows:

- Scenario 1: aligned with prior means
- Scenario 2: high-toxicity scenario
- Scenario 3: low-toxicity scenario
- Scenario 4: very high toxicity scenario
- Scenario 5: low-toxicity followed by high-toxicity

Table 10.3: 2 Assumed true dose-toxicity scenarios

Scenario	P(DLE)	[Redacted]			
		[Redacted]	[Redacted]	[Redacted]	[Redacted]
1: Prior Mean	P(DLE)	0.054	0.073	0.153	0.364
2: High Tox		0.154	0.173	0.243	0.464
3: Low Tox		0.005	0.007	0.053	0.264
4: Very high Tox		0.245	0.353	0.564	0.689
5: Low-High		0.005	0.007	0.243	0.464

The dose level 5 was added for technical reasons, since for simulations at least one dose with assumed true DLE rate in each toxicity interval was required

For each of these scenarios, 1000 trials were simulated. Each cohort consisted of 3 subjects and dose escalation complied with the following rule:

Escalate to the maximum dose which satisfies the overdose criterion and is $\leq 500\%$ increase from the current dose.

The MFD was considered reached if at least 12 subjects have been included in the trial and if at least 6 subjects have been evaluated at a dose level which was the model's recommendation for the next dose. The maximum allowed subject number for each trial was chosen as 18.

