It was then assessed how often a dose was declared as MFD with true DLE rate in the targeted or in the overdosing range. Furthermore, the average, minimum and maximum number of subjects per trial and the average number of DLEs per trial are reported. Results are shown in Table 10.3: 3.

Table 10.3: 3 Simulated operating characteristics

Scenario	% of trials declaring a MFD with true DLE rate in		% of stopped trials*	# Subjects	# DLEs
		overdosing		Mean (Min-Max)	Mean (Min-Max)
1	94.1	2.0	3.9	10.99 (3 - 27)	1.21 (0 - 6)
2	76.2	0.6	23.2	11.39 (3 - 27)	2.14 (0 - 8)
3	99.0	0.8	0.2	9.32 (9 - 27)	0.33 (0 - 5)
4	15.1	18.1	66.8	10.10 (3 - 27)	3.40 (0 - 7)
5	99.9	0.0	0.1	11.84 (9 - 27)	1.37 (0 - 5)

* The stopped trials include early stopped trials (stopped due to too much toxicity), as well as trials that stopped because the maximum allowed subject number was reached before an MFD was found.

In scenario 1, which reflects the case that the true dose-toxicity is aligned with prior mean, 94.1% of the simulated trials declared a dose as MFD with true DLE rate in the targeted toxicity range. Note that 3.9% of the simulated trials stopped either because there was no MFD determined after 27 subjects had been observed or because of too high toxicity for the planned doses.

In scenario 2, the assumed dose toxicities is high. This results in a higher percentage of early stopped trials (about 23.2 %). In this case, about 76.2 % of the trials would end with an estimated MFD within the targeted range, and 0.6 % in the overdosing range.

In Scenario 3 (low-toxicity scenario), only 99.0 % of the trials declared a dose as MFD with true DLE rate in the targeted range. In 0.8 % of the trials, the estimated MFD was in the overdosing range.

Scenario 4 (very-high-toxicity scenario) shows the worst results, i.e. the highest number of stopped trials (66.8 %) and a low number of trials with estimated MFD (15.1 %) in the target range, as would be expected.

Scenarios 5 (low-high toxicity scenario) shows the best results, i.e. the lowest number of stopped trials (0.1 %) and a highest number of trials with estimated MFD (99.9 %) in the target range.

The mean subject numbers ranged from 9.3 subjects (Scenario 3) to 11.8 subjects (Scenario 5), and the maximum number of subjects was 27.

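### Section 7.6 attributes an expected Part A size of about 15 evaluable subjects to the simulation study, but no simulation result supports 15, and the reported table does not follow its own stated rule

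*Protocol*

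**What the plan says.** Protocol Section 7.6 (Part A) states that no formal power calculation was done and gives a range: "a minimum of 3 subjects and a maximum of 18 subjects will be expected for this trial". It adds that fewer may be needed and that the number depends on the cohorts tested. It then cites the simulation study for one central figure, "about 15 evaluable subjects are expected to be treated in the dose escalation part", and ties that figure to reasonable operating characteristics of the MFD recommendation.

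Appendix 10.3 holds the simulation. Its rules are "The MFD was considered reached if at least 12 subjects have been included in the trial", with at least 6 evaluated at the recommended dose, and "The maximum allowed subject number for each trial was chosen as 18". Its results are summarised as "The mean subject numbers ranged from 9.3 subjects (Scenario 3) to 11.8 subjects (Scenario 5), and the maximum number of subjects was 27".

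The design sections point to 12. Section 3.1 plans cohorts of 3, 3 and 6 and includes among the MFD criteria "At least 12 subjects have been treated in the trial". Appendix 10.3 describes the trial without any DLE (hypothetical scenario 13) as proceeding to the top dose "with an additional cohort at that dose level at the end, i.e. overall 12 subjects".

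**The concern.** The sentence in Section 7.6 is the only central size figure offered for Part A, and it makes two claims that can be checked: that the simulation yields about 15, and that about 15 is what the model needs. The simulation it cites reports smaller numbers in every scenario, and the planned path stops at 12. The cited table also appears to come from different rules from those printed above it. A reader therefore cannot tell what size the sponsor expected, or whether the reported operating characteristics belong to the trial as designed.

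**Working it through.** **1. Is 15 in the reported results?** Table 10.3:3 gives mean subject numbers of 10.99, 11.39, 9.32, 10.10 and 11.84 for scenarios 1 to 5. Their average is 53.64 / 5 = 10.73. None reaches 12, and none is near 15.

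**2. Is 15 the planned path?** Cohorts: 3 + 3 + 6 = 12. Hypothetical scenario 13 (no DLE) also totals 12. Hypothetical scenarios 16 to 18 total 3 + 6 + 6 = 15, and 19 to 21 total 6 + 6 + 6 = 18. Each of these includes at least one DLE below the top dose. So 15 is a listed trial size, but not the size reached without DLEs.

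**3. Can the table come from the stated rule?** If every declared MFD needs at least 12 subjects, and every stopped trial has at least one cohort of 3, then

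mean N ≥ (share declaring an MFD) × 12 + (share stopped) × 3.

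The shares are those in Table 10.3:3. The floor is generous, because stopped trials include those that ran to the maximum size.

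| Scenario | Declared | Stopped | Floor on mean N | Printed mean |
|---|---|---|---|---|
| 1 | 94.1 + 2.0 = 96.1% | 3.9% | 11.532 + 0.117 = 11.65 | 10.99 |
| 2 | 76.2 + 0.6 = 76.8% | 23.2% | 9.216 + 0.696 = 9.91 | 11.39 |
| 3 | 99.0 + 0.8 = 99.8% | 0.2% | 11.976 + 0.006 = 11.98 | 9.32 |
| 4 | 15.1 + 18.1 = 33.2% | 66.8% | 3.984 + 2.004 = 5.99 | 10.10 |
| 5 | 99.9 + 0.0 = 99.9% | 0.1% | 11.988 + 0.003 = 11.99 | 11.84 |

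Scenarios 1, 3 and 5 fall below their floors, so the table cannot come from a rule that requires 12. It also shows a maximum of 27 in every row, against the stated cap of 18. This step needs no assumption about doses.

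**4. What does the stated rule give?** I re-simulated the BLRM with the three-component prior of Table 7.1:1, EWOC at 25%, cohorts of 3, and the true rates of Table 10.3:2. The doses are redacted, so only ratios to the reference dose were used. The start-to-top ratio follows from the first prior component: exp[(logit 0.02 − logit 0.10) / exp(0.052)] = exp[(−3.892 + 2.197) / 1.053] = 0.20. A middle ratio of 0.4 reproduces the prior mean of 0.073 and median of 0.027 in Table 7.1:2. A ratio of 2 was assumed for the extra technical dose where that dose was included.

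As a calibration, a minimum of 9, a maximum of 27 and dose skipping came close to the printed table:

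| | Sc. 1 | Sc. 2 | Sc. 3 | Sc. 4 | Sc. 5 |
|---|---|---|---|---|---|
| Mean N, re-run | 11.3 | 10.9 | 9.7 | 9.2 | 11.9 |
| Mean N, printed | 10.99 | 11.39 | 9.32 | 10.10 | 11.84 |
| MFD on target, re-run (%) | 95.2 | 72.5 | 99.3 | 13.4 | 99.9 |
| MFD on target, printed (%) | 94.1 | 76.2 | 99.0 | 15.1 | 99.9 |

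Under the stated rule (at least 12, maximum 18), three planned doses:

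| | Sc. 1 | Sc. 2 | Sc. 3 | Sc. 4 | Sc. 5 |
|---|---|---|---|---|---|
| Mean N, skipping allowed | 12.6 | 11.5 | 12.1 | 9.3 | 13.2 |
| Chance of 15 or more | 24% | 27% | 4% | 19% | 36% |
| Mean N, next planned dose only | 12.7 | 11.4 | 12.2 | 9.1 | 12.9 |
| Chance of 15 or more | 29% | 30% | 5% | 16% | 31% |

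Other versions, including six subjects entered together at the top dose, widen this to roughly 12 to 13.7 in scenarios 1, 3 and 5, 11 to 12 in scenario 2 and 9 to 10 in scenario 4. The chance of reaching 15 or more is then roughly 3 to 50%. No version gives a mean of 15.

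**The case against.** The best defence is that Section 7.6 is loosely worded and harmless. It gives a range of 3 to 18, says fewer may be needed, and makes the number depend on the cohorts tested. Section 7.1 lets the SMC add subjects at the top dose. The figure enters no decision rule, analysis set or test, and the Part A primary endpoint is analysed descriptively. SAP Section 7 describes the BLRM evaluations as already performed, so a correction changes no conduct. All of this stands, and it limits the importance of the point. It does not supply a source for 15: a permitted size is not an expected one, and the sentence names the simulation as its basis.

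Two stronger readings are tempting, and the documents do not support them. A reader might take 9.3 to 11.8 at face value and conclude that Part A falls 20 to 38% short of 15. The lower figures cannot arise under the stated rule, so they do not measure the present design. A reader might also conclude that Part A is too small for its model. The printed table shows 94 to 99.9% of trials declaring an MFD in the target range in scenarios 1, 3 and 5, with only about 9 to 12 subjects. The re-simulation under the stated rule, with three planned doses, gives about 96 to 100% in those scenarios with about 12 to 13.

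**Conclusion.** The point holds as a misstatement of expected size. About 15 is supported neither by the printed results, nor by the planned path of 12, nor by re-simulation of the stated rule. The gap is 3 subjects (20% of 15) on the path without DLEs. It is still about 1.3 subjects (15 − 13.7) at the largest simulated mean. At the finalisation of protocol version 4.0, Section 1.2 reports seven Part A subjects treated and no DLEs, which is consistent with the 12-subject path.

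The underlying defect is that Table 10.3:3 does not match the rules printed with it. Section 11.1 records that Amendment 1 changed the required number from 9 to 12, so the table may predate that change; this is an inference. No loss of performance at 12 to 13 subjects has been shown, and none is claimed.

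The comparison with the printed means and the floor in step 3 rest only on the documents. The re-simulated means rest on inferred dose ratios and carry Monte Carlo error of roughly 0.1 to 0.2 subjects. They show that 15 is not the expected size; they are not replacement figures.

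**What to change.** Re-run Table 10.3:3 under the stated rules: at least 12 subjects to declare an MFD, a maximum of 18, and the protocol's own escalation rule. Section 7.1 (next planned dose, increment limited to 250%) and Appendix 10.3 (up to 500%) describe that rule differently, and the sponsor needs to reconcile them first. Correct the references to 27 subjects in the results text.

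Then restate the sentence in Section 7.6 as the re-simulated mean per scenario, 12 if no DLE occurs, and a maximum of 18. Drop the statement that about 15 are needed for reasonable operating characteristics, unless the re-run supports it.

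The cost is one simulation run, an updated table with its text, and one restated sentence. No extra subjects are needed. The stated figure becomes slightly less favourable. As the Part A escalation analyses are already done, the benefit is to the protocol record and the trial report.
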